number of participants in each of two groups: intervention group (132) and control group (usual care) (132). Since participants will be recruited from only four regions, we will model the effect of region as a fixed effect rather than a random effect.¹⁸ This will allow region-specific intervention effects to be modelled (i.e. region by intervention interaction effects). If no region by intervention interactions are found, the interaction terms will be dropped from the model and we will estimate an overall intervention effect. Since the region by intervention interaction is unknown, we take a conservative approach with a sample size calculation that will enable detection of an intervention effect within each site. This will allow for a properly powered analysis of the site by treatment interaction. The primary outcome measure (Transition Readiness Assessment Questionnaire, TRAQ)⁹ has been validated on a sample of youth with congenital heart disease and in the absence of literature specific to BBD, we will base our sample size calculations on these findings. We anticipate a mean TRAQ self-management baseline score of 3.01 (SD 1.02) (out of a possible 5.0) as reported for youth (with congenital heart disease) without a transition intervention and an anticipated mean score of 4.0 at 6 months post-intervention resulting in a change score of 1 (i.e., 1 SD), with $\alpha=0.05$ and 90% power.¹⁹ Therefore, in each region, we will require 23 youth in each of the 2 arms (total of 46) x 4 regions = 184. Estimating 30% attrition, we will enroll 264 participants.

Inclusion Criteria

- Youth with chronological age between 15 and 17 years of age (i.e. before 18th birthday), in one of the four study regions, followed in pediatric care and for whom a discharge from pediatric care is planned but not for at least 6 months.
- A diagnosis of one of the following neurological BBD: autism spectrum disorder, cerebral palsy, epilepsy, spina bifida, or fetal alcohol spectrum disorder.
- Cognitive ability to provide informed consent and the ability to read and understand English or French
- Access to internet and a smartphone, iPad/tablet or desktop computer.
- TRANSITION-Q²⁰ score >40 (as a screen to define a minimum threshold for transition readiness based on our earlier work).

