analysis begins as soon as data are collected in a study. This iterative approach is imperative, as early and continuous coding drives ongoing data collection (e.g., new questions that arise). The two-week period reflects the average time it would take for a transcriptionist to complete transcription of an audio file. Once a participant's interview becomes part of the analysis, it begins to shape interpretation and meaning of the data. If someone were to request withdrawal of their data after it has been coded, it would be hard to distinguish if something from their interview might have already contributed to our collective understanding of the data. Once the study analysis has been completed, we cannot withdraw data in order to protect the integrity of the research.

Randomization

Randomization will be stratified by region with a 1:1 allocation ratio for patients: intervention group (receiving MyREADY Transition™ BBD App intervention) or control group (continuing with usual care). The unit of randomization is the patient. We will use variable block randomization with block sizes of 2, 4, 6 and 8. Allocation will be done via REDCap (Research Electronic Data Capture)²² using a centralized allocation system generated by the Biostatistics Unit at St. Joseph's Hospital in Hamilton, Ontario.

Participants who meet the eligibility requirements at the point of screening, and who give consent to participate will be randomized to a group. Once a patient has been randomized to the intervention group, the Research IT team at McGill University will receive the assigned study identification number to associate with the user activation code in the MyREADY Transition™ BBD App. The RA at the recruitment site will use the study identification number and user activation code to facilitate the download and user orientation to the App. The RCT Research Coordinator at McMaster University and the Research IT team at McGill University will support the use of the App and troubleshoot issues as they arise. This will be done using a designated email to capture and respond to queries and will include an automated response, indicating receipt and response time.

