Participants randomized into the intervention group will also have an introduction to the MyREADY Transition™ BBD App intervention at the baseline visit. They will be provided with brief verbal and written instructions about how to use and engage with the intervention. The RA will navigate through the MyREADY Transition™ BBD App intervention with the participant to give a short demonstration. The baseline visit for participants in the intervention group will take an estimated one and a half hours to complete in order to ensure that the participants feel able to use the MyREADY Transition™ BBD App intervention. All RAs will receive intervention-facilitation training and treatment fidelity will be monitored.

Follow-Up Visits

Participants will repeat the questionnaire package at 6-months following baseline. The RA will arrange these visits at a mutually convenient time during follow-up appointments in clinic if possible, or otherwise outside of clinic time. If an in-person visit is not possible, the questionnaire package can be completed online, by mail or by phone interview according to the participant's preference.

Qualitative Data Collection

In addition to the quantitative follow-up at 6-months, qualitative data will be collected for a subset of participants using interviews. Up to 50 youth in the intervention group will be interviewed after the 6-

NOTE: CTO#1666 Amendment approved by HiREB on January 9, 2023. Target sample was 264 participants; however, we randomized 52 participants, and did not complete the full-scale RCT. Linking health card numbers with provincial administrative data is labour intensive and costly, and the small number would not provide meaningful results. As approved by ethics, we dropped the health economic outcome analysis (Health card number linking, Health Utilities Index (HUI), Resource Use Questionnaire (RUQ)) and destroy stored health card number data.

month quantitative data collection point to describe and understand primary study outcomes, as well as to capture process and user experience related to the secondary aims. We will purposefully select some participants who have completed only a low percentage of App content to learn about the experiences of those participants.

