The COPM is an evidence-based, generic, and individualized outcome measure used to capture a client's self-perception of performance and satisfaction in everyday living, over time.²⁷ The measure accomplishes this by identifying problems in performing activities of daily living. The patient is encouraged to think about things that they want to do, need to do or are expected to do but can't do, don't do or aren't satisfied with the way they do. Concrete examples are provided for youth: things related to their health and personal care, getting ready for the day, getting around, working, household chores, school, recreation, socializing. The patient is asked to rate current performance of each using a 10-point scale from 'not able to do it' to 'able to do it very well'. The patient is also asked to rate satisfaction with performance on a 10-point scale from 'not satisfied at all' to 'extremely satisfied' with higher scores reflecting better performance and satisfaction with performance as perceived by the patient. The performance and satisfaction can be re-assessed following a period of treatment.²⁸ The COPM will be administered to all youth participants.

TRANSITION-Q²⁰

The TRANSITION-Q is a 14-item transition readiness/self-management ability scale.^{20, 29} This short, clinically meaningful and psychometrically sound scale can be used in research and in pediatric and adolescent clinics to help evaluate readiness for transition.²⁰ Item responses ("never" = 0, "sometimes" = 1, and "always" = 2) are summed to create a raw score, with a possible range from 0 to 28. Raw scores are transformed using a table provided by the developers and the transformed scores range from 0-100. A higher score indicates greater transition readiness; exhibiting more self-management skills with higher frequency.^{20, 30}

A TRANSITION-Q score > 40 will be used as an eligibility screen to define a minimum threshold for transition readiness based on our earlier work. At the point of screening and recruitment, we will evaluate several components of cognitive function as well as youth capacity to share the management of their own health. The TRANSITION-Q screen will inherently exclude youth who have severe intellectual disability, and/or those who rely significantly on parents/caregivers in most areas of daily functioning, self-care and/or communication. We will repeat the TRANSITION-Q at the 6-Month Follow-Up Visit.

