PedsQL™ Pediatric Quality of Life Instrument, Generic Core, Teen Report (13-18 years)¹¹

The PedsQL™ Measurement Model (http://www.pedsql.org/about_pedsql.html) is a modular approach to measuring health-related quality of life (HRQOL) in healthy children and adolescents and those with acute and chronic health conditions.

In this study the PedsQL™ Pediatric Quality of Life Instrument, Generic Core, Teen Report (13-18 years) will be completed by youth participants at Baseline and 6-Months. The form is brief (23 items), practical (less than 4 minutes to complete), multidimensional (Physical, Emotional, Social, School Functioning), reliable (Child Self-Report; 0.90) and valid (Distinguishes between healthy children and children with

NOTE: CTO#1666 Amendment approved by HiREB on January 9, 2023. Target sample was 264 participants; however, we randomized 52 participants, and did not complete the full-scale RCT. Linking health card numbers with provincial administrative data is labour intensive and costly, and the small number would not provide meaningful results. As approved by ethics, we dropped the health economic outcome analysis (Health card number linking, Health Utilities Index (HUI), Resource Use Questionnaire (RUQ)) and destroy stored health card number data.

acute and chronic health conditions; distinguishes disease severity within a chronic health condition), and responsive to clinical change over time.

Patient Activation Measure (PAM) (health-related self-efficacy)³¹

The Patient Activation Measure (PAM) (<http://www.insigniahealth.com/products/pam-survey>) is a valid, reliable, unidimensional, Guttman-like scale based on a developmental model of activation. Activation appears to involve four stages: (1) believing the patient role is important, (2) having the confidence and knowledge necessary to take action, (3) actually taking action to maintain and improve one's health, and (4) staying the course even under stress. The measure has good psychometric properties indicating that it can be used at the individual patient level to tailor intervention and assess changes.³¹

PAM originally included 22 questions, and through subsequent validation of the short-version now has 13 questions. The PAM assesses a patient's confidence in self-managing their condition, and the total score allows individuals to be categorized into four levels:

Level 1 - disengaged and overwhelmed

Level 2 - becoming aware, but still struggling

Level 3 - taking action

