We will request consent to obtain youth participant's Health Card Number to answer questions about use of health services like physician office visits, visits to emergency rooms and hospitalizations during

NOTE: CTO#1666 Amendment approved by HiREB on January 9, 2023. Target sample was 264 participants; however, we randomized 52 participants, and did not complete the full-scale RCT. Linking health card numbers with provincial administrative data is labour intensive and costly, and the small number would not provide meaningful results. As approved by ethics, we dropped the health economic outcome analysis (Health card number linking, Health Utilities Index (HUI), Resource Use Questionnaire (RUQ)) and destroy stored health card number data.

the study period (between the time a participant joins the study up until March 31, 2021). Participants have the option of participating in the study without sharing the youth's Health Card Number. The Health Card Number will allow us to link the information provided in the study with provincial data regarding the participant's use of health services. We will work with appropriate organizations in each province (Alberta, Ontario, Quebec, New Brunswick, and Nova Scotia) to gain approval to access provincial Health Services Administrative Data repositories. Health care services data recorded in the provincial administrative databases will be linked deterministically to the study data using the Health Card Number, partial date of birth and sex.

STATISTICAL ANALYSIS:

We will use regression analysis to adjust for baseline function as a sensitivity analysis to address any residual imbalance from the randomization.

The analysis and reporting of the internal pilot phase and main RCT results will follow CONSORT guidelines²³⁻²⁴. Patient demographics and baseline outcome variables (both primary and secondary) will be summarized using descriptive summary measures. All analyses will be performed using SAS 9.4 (Cary, NC). Analysis will be intention to treat. The table below provides a summary of study objectives, corresponding outcomes, hypotheses and methods of analyses. For subgroup analysis we will use interaction test (interaction of subgroup variable with the treatment or intervention variable).

Table 1: Study Objectives, Corresponding Outcomes, Hypotheses and Methods of Analyses

Objective	Outcome	Criterion for Success	Method of Analysis

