Primary: To determine whether the MyREADY Transition™ BBD App intervention will result in improved transition readiness	Primary: 
 Change in TRAQ self-management score from Baseline to 6 months. 	Intervention > Control	T-Test; p<0.05
	Secondary: 
 Change in TRAQ self-advocacy score from Baseline to 6 months. 	Intervention > Control	T-Test; p<0.05
	Secondary 
 Health care transition experience 	Individual semi-structured interviews	Qualitative Methods
Secondary: What is the effect of the MyREADY Transition™ BBD App intervention for	Primary: Population Health 
 Serious illness (hospitalizations, ICU admission questions from Resource Use Questionnaire 	Intervention > Control	T-Test for continuous outcomes Chi-square test

NOTE: CTO#1666 Amendment approved by HiREB on January 9, 2023. Target sample was 264 participants; however, we randomized 52 participants, and did not complete the full-scale RCT. Linking health card numbers with provincial administrative data is labour intensive and costly, and the small number would not provide meaningful results. As approved by ethics, we dropped the health economic outcome analysis (Health card number linking, Health Utilities Index (HUI), Resource Use Questionnaire (RUQ)) and destroy stored health card number data.

improving health and use of health systems?	
 • PedsQL™ Pediatric Quality of Life • Patient Activation Measure (PAM) (health-related self-efficacy) • TRANSITION-Q 		for hospitalization
	Secondary: 
 • Utilization MyREADY Transition™ BBD App 	User metrics built into MyREADY Transition™ BBD App intervention to assess the extent to which various components of the intervention are accessed	Descriptive
	Secondary: Cost utility/cost-effectiveness 
 • Health Utilities Index® (Hui2/3) • Resource Use Questionnaire 	Evaluate changes in patients' health in relation to changes in cost to assess if the intervention represents an efficient allocation of health care resources	Descriptive; Cost-effectiveness analysis with support from Child-Bright health economics network team

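### For PedsQL, PAM and TRANSITION-Q, Table 1 makes an unadjusted t-test the main analysis although entry scores are collected; ANCOVA on the entry score and region would be more precise

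*Combined protocol and SAP*

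**What the plan says.** **Main analysis.** In Table 1, the Population Health row under the secondary objective lists PedsQL, PAM and TRANSITION-Q by name and gives the method as "T-Test for continuous outcomes". It mentions no covariate, and neither a change score nor a 6-month score. The two TRAQ rows of the same table do specify change from baseline to 6 months.

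**Entry scores.**
- PedsQL (Secondary Measures): "will be completed by youth participants at Baseline and 6-Months".
- TRANSITION-Q (Secondary Measures): scored at the eligibility screen, where it must exceed 40, and then "We will repeat the TRANSITION-Q at the 6-Month Follow-Up Visit".
- PAM: its own section gives no time points. They follow from Follow-Up Visits: "Participants will repeat the questionnaire package at 6-months following baseline".

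**Baseline adjustment.** The Statistical Analysis section opens with "We will use regression analysis to adjust for baseline function as a sensitivity analysis to address any residual imbalance from the randomization". It names neither the covariate nor the outcomes covered.

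**Region.** Under Randomization: "Randomization will be stratified by region with a 1:1 allocation ratio for patients". The Synopsis says the outcome metrics will be analysed stratified by region. The Sample section, in the text that sizes the trial on TRAQ, says "we will model the effect of region as a fixed effect rather than a random effect". Table 1 has no region term.

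**The concern.** Each of these scales has an entry score that is likely to predict the 6-month score. A t-test on 6-month scores does not use it. A t-test on change uses it with a fixed weight of 1, which is not the most precise weight when the correlation is below 1. In both cases the main estimate has a wider confidence interval than the collected data allow, and any chance difference in entry scores between arms is either left in or over-corrected. The planned regression would deal with this, but it ranks second and the plan gives no reason for that order.

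This matters more because only 52 of the intended 264 youth were randomised, so precision is scarce and chance differences at entry are larger than planned. Leaving the score undefined also means that two analysts could follow Table 1 and report different results.

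**Working it through.** **Inputs from the documents.** TRAQ sizing: SD 1.02, difference 1, alpha 0.05, power 90%, 23 per arm per region, 184 evaluable, 30% attrition, 264 enrolled. Actual: 52 randomised, so about 26 per arm, or 52 × 0.7 = 36.4, about 18 per arm, if the planned attrition occurs.

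**Assumptions, because the documents give none for these scales.** Correlation rho between entry and 6-month score of 0.3 to 0.7; true difference 0.5 SD; two-sided alpha 0.05.

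**1. The plan's own figure, to check the method.** Two-sided noncentral-t power for a difference of 1, SD 1.02 and 23 per arm is 90.2%, so 23 per arm reproduces. Attrition: 46/0.7 = 65.7, rounded up to 66 per region; 66 × 4 = 264. This is a TRAQ calculation. No size or power is stated for PedsQL, PAM or TRANSITION-Q.

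**2. Residual variance, relative to a t-test on 6-month scores.**

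| rho | 6-month t-test: 1 | Change t-test: 2(1 − rho) | ANCOVA: 1 − rho² | ANCOVA / change: (1 + rho)/2 |
|---|---|---|---|---|
| 0.3 | 1 | 1.40 | 0.91 | 0.65 |
| 0.5 | 1 | 1.00 | 0.75 | 0.75 |
| 0.7 | 1 | 0.60 | 0.51 | 0.85 |

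Which t-test is better depends on rho: the 6-month score below 0.5, the change score above it. ANCOVA has the smaller variance throughout the range.

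**3. Power at 0.5 SD.** The closed-form figures use the noncentral t with the variances above. For ANCOVA, four error degrees of freedom are removed (one for the entry score, three for region). The formula omits the small cost of chance covariate imbalance, so the last column simulates the full model with balanced arms within four regions and no true region effect.

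| Per arm | rho | 6-month t-test | Change t-test | ANCOVA, formula | ANCOVA, simulated |
|---|---|---|---|---|---|
| 26 | 0.3 | 42% | 32% | 46% | 45% |
| 26 | 0.5 | 42% | 42% | 53% | 53% |
| 26 | 0.7 | 42% | 63% | 70% | 68% |
| 18 | 0.3 | 31% | 23% | 33% | 32% |
| 18 | 0.5 | 31% | 31% | 39% | 37% |

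At 18 per arm the simulated gain over the 6-month t-test is about 1 point at rho 0.3 and about 7 at rho 0.5 (30.8% to 37.3%). At the planned 92 per arm the 6-month t-test has 92% and ANCOVA 94%, 97% and 99.7%, so the choice would have mattered less at full size.

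**4. Chance imbalance at entry.** The SD of the difference between arms in mean entry score is √(2/n) in SD units: √(2/26) = 0.28 and √(2/18) = 0.33. The probability of a difference beyond 0.3 SD in either direction is 28% and 37%.

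**5. Region.** If region explains 5% or 10% of the variance, adjusting for it moves power at 26 per arm from 42% to 44% or 46%. Simulated type I error of the t-test that ignores region is 4.4% and 4.0% (23 per arm per region), slightly conservative.

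**The case against.** **The unadjusted test is legitimate, and adjustment is already planned.** Both are true. Randomisation makes the t-test unbiased on average, and the regression is in the plan. What remains is which analysis leads, and for these scales the plan leads with the less precise one without giving a reason.

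**The t-test may be on change.** This is a fair reading, since the TRAQ rows and the trial hypothesis use change. A reader might infer that the entry score is simply thrown away; the row is silent, so that cannot be asserted. If change is meant, the saving from ANCOVA is 1 − 0.85 = 15% at rho 0.7, rather than the 49% that applies against a 6-month comparison. It is still a saving.

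**Region is not ignored by the plan.** A reader of Table 1 alone might infer that it is. The Synopsis and Sample sections show otherwise, although the Sample wording sits in the TRAQ sizing text and is not clearly extended to these scales. This is an inconsistency to reconcile, and blocking within region already keeps the arms close to balance.

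**The gain cannot be sized from the documents.** This stands. The power figures rest on assumed correlations and an assumed effect. The TRANSITION-Q rule of more than 40 cuts off the lower range of entry scores, which may lower that scale's correlation and so its gain.

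**Baseline may not precede allocation.** Randomization requires screening and consent, without stating that the baseline questionnaires come first, and the App is introduced at the baseline visit. This is a proper caution for PedsQL and PAM. It does not favour the alternative, because a change score would rest on the same baseline.

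**Conclusion.** The point holds as one of efficiency and specification in three secondary outcomes. Table 1 does not define the score being compared and leads with an unadjusted test; ANCOVA is more precise than either version of that test for every correlation from 0.3 to 0.7. On the assumed 0.5 SD difference and 26 per arm, the gain over a 6-month t-test runs from about 3 points of power at rho 0.3 to about 26 at 0.7. Over a change-score t-test it is about 13 points at 0.3 and 5 to 7 at 0.7. With 18 per arm and a low correlation it nearly vanishes, and at rho 0.3 to 0.5 these comparisons remain underpowered under any of the three analyses.

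Two stronger readings are not supported. A reader might infer that the trial's main result is affected; the primary outcome is change in TRAQ self-management, which has its own row. A reader might also infer that chance imbalance biases the comparison; it costs precision, and on average over randomisations it introduces no bias.

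**What to change.** In Table 1, for PedsQL, PAM and TRANSITION-Q, replace the t-test entry with wording such as: *ANCOVA of the 6-month score on arm, the same scale's entry score (the screening score for TRANSITION-Q) and region; adjusted mean difference with 95% confidence interval.* Keep the unadjusted t-test as a supportive analysis, and state whether it uses the 6-month or the change score.

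Align Table 1 with the Synopsis and Sample text on region, and with the opening sentence of Statistical Analysis, saying which covariate and which outcomes that regression covers.

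No new data are needed, and the model uses four extra degrees of freedom. The cost is procedural. Recruitment has ended, so the change should be documented with its reason before any unblinded analysis. The team should also confirm from the records that PedsQL and PAM baselines were completed before participants learned their allocation, and report any that were not.

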	Secondary: 
 • Achievement of health/life goals • Canadian Occupational Performance Measure (COPM) 	Intervention > Control	Paired Student t-tests to compare mean ratings for performance and satisfaction on the COPM scoring system (10-point scale) with > 2 points difference as clinically meaningful difference

Qualitative Data Analysis

In this study, individual interviews will be audio-recorded and transcribed verbatim. Data will be stored and managed electronically using NVivo® Version 11³⁶, a qualitative research data management

NOTE: CTO#1666 Amendment approved by HiREB on January 9, 2023. Target sample was 264 participants; however, we randomized 52 participants, and did not complete the full-scale RCT. Linking health card numbers with provincial administrative data is labour intensive and costly, and the small number would not provide meaningful results. As approved by ethics, we dropped the health economic outcome analysis (Health card number linking, Health Utilities Index (HUI), Resource Use Questionnaire (RUQ)) and destroy stored health card number data.

software program to facilitate the organization and coding of large quantities of data. Conventional content analysis ³⁷ will be used to code, categorize and synthesize the data to contextualize the analysis of the primary aim of the RCT. In addition, data related to usability of the App will be monitored and analyzed by the Research IT team at McGill to inform ongoing App development.

Health Economic Evaluation

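### The COPM row of Table 1 requires superiority over control but names only paired t-tests, which compare each youth with themselves and cannot test that

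*Combined protocol and SAP*

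**What the plan says.** In Table 1 (Statistical Analysis), the COPM row sets superiority of the intervention arm over the control arm as the criterion for success. Its method cell reads "Paired Student t-tests to compare mean ratings for performance and satisfaction on the COPM scoring system (10-point scale" and continues "with > 2 points difference as clinically meaningful difference". The row names no other test.

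The relevant text elsewhere is:

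- **Randomization section:** "Randomization will be stratified by region with a 1:1 allocation ratio for patients". The unit is the individual patient and no matching is described.
- **COPM description (Study Measures):** "The COPM will be administered to all youth participants", and "The performance and satisfaction can be re-assessed following a period of treatment".
- **Follow-Up Visits:** "Participants will repeat the questionnaire package at 6-months following baseline".
- **Table 1, health outcomes such as PedsQL and PAM:** the same superiority criterion, with "T-Test for continuous outcomes". The TRAQ rows also give a t-test that is not called paired.
- **Opening of Statistical Analysis:** "We will use regression analysis to adjust for baseline function as a sensitivity analysis to address any residual imbalance from the randomization".

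The January 2023 amendment note drops the health economic measures. It does not list the COPM, so this row still applies.

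**The concern.** A paired t-test needs linked observations. Without matching across arms, the only links are between one youth's ratings at two times. The test then asks whether ratings changed, whereas the criterion asks whether they changed more with the App than without it.

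The COPM is particularly exposed to this. Youth name activities that they cannot do, do not do or are dissatisfied with, and then rate them. Problems chosen because they are rated poorly can be rated higher later through regression to the mean, maturation or usual care. A between-arm comparison removes such shared gains; a within-arm test counts them. If a significant paired test is read against the stated criterion, a gain that the control arm also made could be reported as an App effect.

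The threshold of more than 2 points is also undefined. It could be a change within one youth, a mean change within an arm, or a difference between arms.

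**Working it through.** **The plan's own figures.** The plan gives no sample size, expected gain or SD for the COPM. Its sizing is for the TRAQ. That reproduces: a t-based two-sample calculation with difference 1, SD 1.02, two-sided α = 0.05 and 90% power gives 22.87, so 23 per arm per region. Then 23/0.70 rounds up to 33, and 33 × 8 = 264. It does not bear on this point.

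**Inputs for the illustration**

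- Number randomised: 52 (amendment note). An even split, 26 per arm, is assumed from the 1:1 ratio.
- With the plan's 30% attrition: 26 × 0.70 = 18.2, so 18 per arm.
- Shared gain in both arms: 0.5 to 2 points (assumed).
- SD of change: 2, 2.5 or 3 points (assumed).
- App effect: none.

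**Step 1: paired test in the App arm.** With gain g, SD s and n youth, the t statistic is noncentral t with n − 1 degrees of freedom and noncentrality (g/s)√n. A two-sided 5% test shows improvement when it exceeds 2.060 (n = 26) or 2.110 (n = 18). For g = 1, s = 2 and n = 26, the noncentrality is 0.5 × 5.099 = 2.550 and the probability is 0.688.

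| Youth per arm | Shared gain | SD 2 | SD 2.5 | SD 3 |
|---|---|---|---|---|
| 26 | 1 | 0.688 | 0.500 | 0.372 |
| 26 | 0.5 | 0.232 | 0.164 | 0.127 |
| 18 | 1 | 0.516 | 0.360 | 0.266 |

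**Step 2: two-sample test on change.** The shared gain cancels, so the chance of a significant result favouring the App is the nominal 0.025. Simulation (200,000 trials per cell) gives 0.024 to 0.026.

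**Step 3: one paired test per arm, with success read as App significant and control not.** If p is the Step 1 probability and the arms are independent, the chance is p(1 − p). At 26 per arm:

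- gain 1: 0.688 × 0.312 = 0.215; 0.500 × 0.500 = 0.250; 0.372 × 0.628 = 0.234;
- gain 0.5: 0.178, 0.137 and 0.111.

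The maximum is 0.25. When the shared gain is large, both arms are usually significant and the pattern becomes rare (0.002 for gain 2 and SD 2). A real App effect would then be hidden too, so this reading does not test the criterion either.

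**Step 4: also require the App arm's mean change to exceed 2 points.** Simulated chance that both conditions hold, for SD 2, 2.5 and 3:

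- 26 per arm, gain 1: 0.006, 0.021, 0.043;
- 26 per arm, gain 1.5: 0.101, 0.155, 0.198;
- 26 per arm, gain 2: about 0.50 throughout;
- 18 per arm, gain 1: 0.017, 0.045, 0.080.

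Normal check for 26 per arm, gain 1 and SD 2: the standard error is 2/5.099 = 0.392, (2 − 1)/0.392 = 2.55, and the upper tail is 0.005.

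**The case against.** The best defence is that this is a wording slip. No other t-test in Table 1 is called paired, and the author may have meant a between-arm t-test on each youth's change. That is plausible, but the current text does not say it, and an analyst following the table would run a different test.

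Second, the highest rates treat a significant result in the App arm alone as success, which the plan does not state. The row refers to tests in the plural and the COPM goes to both arms, so one test per arm is a natural reading. This objection lowers the headline figure: Step 3 gives 11% to 25% for gains of 0.5 to 1 point at 26 per arm. Those rates are still well above 2.5%.

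Third, the baseline-adjusted regression names no outcome at all, so it could be applied to the COPM and would yield a between-arm estimate. That is a partial safeguard. It is labelled a sensitivity analysis and does not replace the test in the row. The region model in the Sample section belongs to the TRAQ sizing and does not mention the COPM.

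Fourth, every gain and SD used here is assumed, and a strict 2-point rule can bring the error close to nominal. Both points stand. The calculation shows how the error arises and how far it could range; it does not predict its size in this trial.

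**Conclusion.** The concern holds. As written, the method in the COPM row cannot test the criterion in the same row, and no other part of the document corrects it. That conclusion follows from the design and needs none of the assumed numbers.

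The practical size depends on the shared gain, the SD of change, and the meaning of the 2-point threshold. At 26 per arm with gains of 0.5 to 1 point, the false-positive rate is 13% to 69% if the App arm is tested alone, and 11% to 25% if each arm is tested and the results compared. Adding a requirement that the arm's mean change exceed 2 points gives 0.5% to 4% for a 1-point gain, rising to about 50% for a 2-point gain. A between-arm test stays at 2.5% throughout.

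The COPM is a secondary outcome. The TRAQ analysis and the sample size are untouched. It should be fixed, but it does not threaten the trial's main result.

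**What to change.** In the COPM row of Table 1, replace the paired tests with a between-arm comparison, made separately for performance and satisfaction. The minimum is an independent two-sample t-test on change from baseline to 6 months. Preferable, though not needed to cure the fault, is a regression of the 6-month rating on arm, baseline rating and region. Report the between-arm difference with its 95% confidence interval, and keep within-arm changes as description only.

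Add one sentence saying whether the 2-point threshold refers to change within a youth or to a difference between arms, and whether it is part of the success criterion or only an aid to interpretation.

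The cost is one table cell, one sentence and routine code. No new data should be needed, since all youth receive the COPM and the questionnaire package is repeated at 6 months. The COPM description gives no follow-up time of its own, so the 6-month rating is inferred from the Follow-Up Visits section and is worth stating explicitly in the same edit.
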